4.2 Endpoint(s)

Primary Endpoint

- Incidence rate of FVIII inhibitors (≥ 0.6 BU/mL)

Secondary Endpoint(s)

Safety Endpoints:

- Frequency of adverse events (AEs) and serious adverse events (SAEs) reported during the trial period
- Incidence rate of clinically relevant inhibitors defined as an inhibitor titre (≥ 0.6 BU/mL) combined with a decreased recovery (<66% of expected level)
- Incidence rate of high-titre inhibitors defined as inhibitor titre ≥ 5 BU/mL

Efficacy Endpoints:

- Haemostatic effect of N8 on treatment of bleeds assessed on a predefined four point scale: Excellent, Good, Moderate and None
- Annualized bleeding rate
- Number of N8 infusions required per bleed
- Total consumption of N8 per patient (prevention, treatment of bleeds and during surgery) per month and annualised value
- Consumption of N8 (IU/kg/bleed) per bleed
- Consumption of N8 (IU/kg/ months) for bleed prevention

Patient Reported Outcomes (PRO) and Health Economics (HE) End points:

- Change in total scores for parent reported treatment satisfaction
- Health resource utilisation and caregiver burden associated with bleeds

5 Trial Design

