The time interval from last N8 dose to start of a bleed will be summarised. This will be done by a frequency tables dividing the time interval into the following 5 groups: ≤ 12 hrs, > 12 hrs and ≤ 24 hrs, > 24 hrs and ≤ 48 hrs, > 48 hrs ≤ 72 hrs, > 72 hrs. The time interval from last N8 dose to start of a bleed will also be illustrated graphically with time from last dose on the x-axis and number of bleedings on the y-axis.

- Number of N8 infusions required per bleed

The number of infusions of N8 required per bleed will be calculated as the number of infusions of N8 used in the time period from start of the bleed to stop of the bleed. The number of infusions will be presented using count and percentages of all bleeds.

- Total consumption of N8 per patient (prevention, treatment of bleeds and during surgery) per month and annualised value

Total consumption of N8 during the trial will be summarised and listed by patient.

- N8 consumption per bleed

The consumption of N8 (IU/kg BW/bleed) will be calculated as the consumption of N8 used from start of the bleed to stop of the bleed. The consumption will be summarised and listed by patient.

- N8 consumption during bleeding prevention period

The consumption of N8 during bleeding prevention period (IU/kg BW/month) will be calculated as the consumption of preventive N8 doses and summarised and listed by patient.

Secondary Safety Endpoints

- Frequency of adverse events and serious adverse events

All AEs and SAEs will be summarised by frequency of events and frequency of patients with any event. Similar summaries cross-classified by severity and by causal relation to trial product will also be made.

Furthermore, listings will be provided displaying all AEs and SAEs including pertinent clinical information.

- Incidence rate of high-titre inhibitors defined as inhibitor titre ≥ 5 Bethesda units/mL

Incidence rate of high-titre inhibitors will be calculated and a 1-sided 97.5% upper confidence limit will be provided based on an exact calculation for a binomial distribution.

- Incidence rate of clinically relevant inhibitors defined as an inhibitor titre (≥ 0.6 BU/mL) combined with a decreased recovery (<66% of expected level)

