Primary Endpoint

- Incidence rate of FVIII inhibitors (≥ 0.6 BU/mL) will be evaluated for the main phase of the trial

Secondary Endpoint(s)

The secondary endpoints will be evaluated for the main phase of trial, for the extension phase of trial, and for the combined main and extension phases..

Safety Endpoints:

- ---
- Incidence rate of FVIII inhibitors (≥ 0.6 BU/mL).

2.7 5.1 Type of Trial

The trial comprises 5 planned visits consists of two phases i.e. main and extension, respectively. In the main phase the patients will attend a screening visit (Visit 1) in order to assess their eligibility. At Visit 2 eligible patient will receive their first dose, if applicable, and will be scheduled to attend for 3 more visits. After Visit 5 the patients will enter the extension phase, and a rolling visit schedule will apply with 6 planned visits (including 4 dispensing visits) per year.

The *main trial phase will be completed when the aggregated number of patients will be scheduled to*, who have either received treatment with turoctocog alfa for at least 50 ED or developed inhibitors, are at least 50. ~~which~~ For the individual patient it translates into duration of the *main phase* of approximately 3-24 months depending on the dose regimens (and bleeding pattern). The duration of the extension phase may be up to 3.5 years, and the total duration of the trial is estimated to be approximately 50 months years, please see Section 7.

Patients who develop inhibitors during the trial may continue treatment with turoctocog alfa and will follow an alternative visit schedule, see Section 5.3.4. *These patients will be considered as a separate cohort and will be evaluated accordingly, please refer to Section 18.2.2.*

Details on the trial design can be found in Figure 2-1 and details on the individual visits can be found in Table 2-1 and 2-2, and in Section 8.

2.8 5.3 Treatment of Patients

Approximately 60 patients are expected to be enroled into the trial in order to have 50 *evaluable* patients ~~completing in the main phase of the trial~~ (estimated dropout rate is 15-20%). For replacement of withdrawn patients, please refer to Section 6.5.

The maximum duration of treatment of a patient from first to last turoctocog alfa administration is approximately 24-4 years month.

2.9 5.3.2 Treatment of Bleeds and Dose Adjustment

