- *Incidence rate of inhibitors defined as inhibitor titres ≥ 0.6 Bethesda units/mL for the extension part of trial and the combined main and extension phases of the trial.*

The incidence rate of inhibitors will be calculated and analyzed in the similar way as the primary endpoint.

Furthermore, Kaplan Meyer plots and the additional analyses outlined in Section 18.2.2 for the primary endpoint will be generated using data from the extension phase and the combined main and extension phases of the trial.

- *Frequency of AEs adverse events and SAEs serious adverse events*

AEs and SAEs will be analyzed for the main phase of the trial and the combined main and extension phases.

Separate reports and listings will be made for AEs and SAEs for patients developing inhibitors. Data used in these reports and listings will include data from the first time patient is confirmed with inhibitors until the end of the main phase of trial as well as until the end of trial.

The incidence rate of clinically relevant inhibitors and high-titre inhibitors will be evaluated for the main phase of trial, for the extension phase of trial, and for the combined main and extension phases.

All additional safety parameters such as laboratory parameters and physical examinations will be listed and summarized by visit for all patients for the main phase of trial, for the extension phase of trial, and for the combined main and extension phases

Separate reports and listings will be made for the above safety endpoints for patients developing inhibitors. Data used in these reports and listings will include data from the first time patient is confirmed with inhibitors until the end of the main phase of trial as well as until the end of trial.

2.45 18.6 Health Economics and Patient Reported Outcomes

Health economic data will be collected in the eCRF in connection with severe bleeds. Patient reported outcomes will be collected using questionnaires at Visits 3 and 5 *in the main phase, and annually during the extension phase.*

2.46 23 Responsibilities

The following will be analysed at the local laboratory: haematology, FVIII trough level assessment and CD4+ T-cell (*excluding Russia*).

~~A~~Central and specialized laboratories will analyse and report all laboratory safety tests related to biochemistry, viral antibody assessments, FVIII activity, FVIII inhibitor assessments and *potential genotyping* performed in this trial.

2.47 27 References

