Screening will be done at Visit 1. Visit 2 will be performed within 21 days post Visit 1, and it could be the same day as Visit 1. At Visit 2 eligible patients are enrolled and preventive treatment with investigational product (turoctocog alfa) starts if applicable (may be delayed, see section 5.3.1 start after the first two bleeds). At Visit 5, after \geq 50 ED, patients will leave the main phase of the trial and continue in the extension phase. Patients who develop inhibitors can continue with ITI treatment with an alternative visit schedule (down ward arrows). If ITI treatment is successful these patients can continue with preventive treatment according to the extension phase (upward arrows). The patients will belong to either of the groups main phase, extension phase or inhibitor cohort.

2.3 5.1 Type of Trial

The main trial phase will be completed when the aggregated number of patients, who have either received treatment with turoctocog alfa for at least 50 ED or developed inhibitors, are at least 50. In the extension phase, *at least 50* the patients will be followed until at least 100 ED has been achieved. For the individual patient it translates into duration of the main phase of approximately 3-24 months depending on the dose regimens (and bleeding pattern). The duration of the extension phase may be up to 3.5 years, and the total duration of the trial is estimated to be approximately 5-7 years, please see Section 7.

2.4 5.3 Treatment of Patients

Patients will enter a bleeding preventive regimen as described below, see Section 5.3.1. ~~Preventive treatment can be postponed until a maximum of two bleeding episodes have occurred.~~ For prevention one single bolus dose of turoctocog alfa is administered intravenously (i.v.) at each administration day. Turoctocog alfa should preferably be administered in the morning. The maximum duration of treatment of a patient from first to last turoctocog alfa administration is approximately 4 years.

2.5 5.3.1 Preventive Treatment and Dose Adjustment

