During the course of the trial, the Monitor will visit the trial site to ensure that the protocol has been adhered to, that all issues have been recorded, to perform source data verification and to monitor drug accountability. *The first monitoring visit will be performed as soon as possible after FPFV and no later than 4 weeks after.* The visit intervals will depend on the outcome of the remote monitoring of the eCRFs, the trial site's recruitment rate, and the compliance of the trial site to the protocol and GCP, ~~but~~ and must not exceed 12 weeks *after preventive treatment has been commenced. Prior to initiation of preventive treatment monitoring should be performed when a patient has been screened and after each treatment requiring bleed.*

2.37 18.2.1 General Considerations

The main CTR will be conducted when at least 50 patients have completed the main phase of the trial (completed visit 5 or has a confirmed inhibitor). The main CTR will present data for the main phase, the extension phase and the combined main and extension phases of the trial. An updated CTR will be conducted when all patients have completed the extension phase of the trial. The updated CTR will also present data for the main phase, the extension phase and the combined main and extension phases of the trial.

2.38 18.4 Explorative Statistical Analysis for Pharmacogenetics and Biomarkers

The data from genotyping and immunogenicity assessment will be summarised using descriptive statistics.

2.39 19.1 Informed Consent Form for Trial Patients

Prior to any trial-related activity, the Investigator must give the patient and/or the patient's LAR oral and written information about the trial in a form that the patient or the patient's LAR can read and understand. This includes the use of impartial witness where required. ~~In this trial the notion of~~

~~legal representative should be understood as both parents, or legal representative(s), as defined in Member States' national laws, who consents on behalf of the child.~~

Consent: As a child is unable to provide legally binding consent, informed consent must be sought from the parents/ legal representative (see definition above) on the child's behalf. The specific and written informed consent of the parents/legal representative must be sought prior to enrolling a child in the trial. Information should be given by an experienced Investigator to each parent, or the legal representative, on the purpose of the trial and its nature.

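### The AE/SAE analysis in Section 18.2.4 leaves out the extension-only period that Sections 4.2 and 18.2.1 call for, and plans crude counts with no adjustment for follow-up

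*Combined protocol and SAP*

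**What the plan says.** AE and SAE frequency is a secondary safety endpoint in protocol Section 4.2: "Frequency of adverse events (AEs) and serious adverse events (SAEs) reported during the trial period". The substantial amendment that split the trial into a main and an extension phase added a general rule to the same section: "The secondary endpoints will be evaluated for the main phase of trial, for the extension phase of trial", and also for the two phases combined.

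That amendment also revised Section 18.2.4. For adverse events the new sentence is "AEs and SAEs will be analyzed for the main phase of the trial and the combined main and extension phases". The neighbouring safety items in the section name all three periods. For example, "The incidence rate of clinically relevant inhibitors and high-titre inhibitors will be evaluated for the main phase of trial, for the extension phase" and for both phases together; the laboratory and physical-examination sentence does the same.

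The summary measure comes from Section 18.2.4 of protocol version 1.0, and none of the amendment texts provided changes it: "All AEs and SAEs will be summarised by frequency of events and frequency of patients with any event". Cross-tabulations by severity and causality, and listings of all events, are planned as well. No denominator of time or exposure days (ED) is given.

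Amendment 7 later added general reporting text to Section 18.2.1: "The main CTR will present data for the main phase, the extension phase and the combined main and extension phases of the trial". It says the same of the updated report.

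**The concern.** Two provisions call for an extension-phase presentation of AEs, and the one sentence specific to AEs does not include it. The programmer who builds the tables will most likely follow the specific sentence.

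The second issue is the measure. Counts of events and of patients with any event grow with follow-up even when the underlying rate is constant. Section 5.1 gives a main phase of about 3 to 24 months and an extension of up to 3.5 years, so the main and combined columns cover very different lengths of observation. Evaluating safety is the trial's primary objective, and one thing the extension can add is whether AEs become more or less frequent as exposure lengthens. The planned summary tables would not show that.

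**Working it through.** The documents give no expected AE rate or other figure for this analysis, so there is nothing to reproduce. The check compares the texts and then illustrates the effect of follow-up.

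**1. Periods named for AEs and SAEs**

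| Source | Main | Extension | Combined |
|---|---|---|---|
| Section 4.2, all secondary endpoints | yes | yes | yes |
| Section 18.2.4, AE/SAE sentence | yes | no | yes |
| Section 18.2.4, clinically relevant and high-titre inhibitors; laboratory and physical examination | yes | yes | yes |
| Section 18.2.1 (Amendment 7), both reports | yes | yes | yes |

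The first two rows come from the same amendment, so this is not a difference between superseded and current text.

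**2. What subtraction can recover.** Extension events = combined events − main events, so the event count is recoverable. The patient count is not, because a patient with an event in both phases counts once in the combined table. Suppose 20 patients have an AE in the main phase and 35 in the combined period. The number with an extension-phase AE then lies between 35 − 20 = 15 (no main-phase patient has another event) and 15 + 20 = 35 (all of them do).

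**3. Effect of follow-up on crude proportions.** Inputs from the documents: main phase up to 24 months (Section 5.1). For maximum treatment per patient I use 5 years, reading the last amendment to Section 5.3 as replacing about 4 years by about 5; the strike-through is lost in the text, so this is an assumption. Also assumed: a constant AE rate λ between 0.1 and 1.0 per patient-year. P(any AE by t) = 1 − exp(−λt).

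| λ per patient-year | t = 2 years | t = 5 years |
|---|---|---|
| 0.1 | 1 − exp(−0.2) = 18% | 1 − exp(−0.5) = 39% |
| 0.5 | 1 − exp(−1.0) = 63% | 1 − exp(−2.5) = 92% |
| 1.0 | 1 − exp(−2.0) = 86% | 1 − exp(−5.0) = 99% |

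Within each row the rate is unchanged; only follow-up differs. Both columns take the longest follow-up the documents allow, so they are upper bounds.

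**4. A falling rate would be hidden.** Assume 0.5 AE per patient-year over 1 year of main phase and 0.25 over 3 years of extension.

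- Events per patient: main 0.5 × 1 = 0.50; combined 0.50 + 0.25 × 3 = 1.25.
- Patients with any AE: main 1 − exp(−0.50) = 39%; combined 1 − exp(−1.25) = 71%.
- Events per patient-year: main 0.50; extension 0.25; combined 1.25 / 4 = 0.31.

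The crude figures rise although the rate has halved. The exposure-adjusted rates show the fall.

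**5. The same question on the ED scale.** The main phase ends at about 50 ED for patients without inhibitors, and the trial asks for at least 100 ED in total. Combined exposure is therefore at least about 100 / 50 = 2 times main-phase exposure for a patient who reaches both marks. The direction is the same on either scale.

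**The case against.** The strongest reply is that this is a drafting slip. Sections 4.2 and 18.2.1 both point to an extension-phase presentation, and the neighbouring safety endpoints include it. The documents are a base protocol with amendment change sheets rather than a consolidated final text, and several amendments report correcting minor inconsistencies without listing each one, so the sentence may since have been aligned. This stands as far as intent goes, and it is why the point is a reconciliation. It does not settle what the AE tables will contain, since no text provided changes the AE sentence, and it does not touch the lack of a denominator.

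It can also be said that exposure-adjusted rates are optional in a single-arm trial with no hypothesis testing, that no comparison of main with combined is planned, and that the primary safety endpoint, inhibitors, already has Kaplan-Meier plots. That is fair, and it keeps the priority low. However, the plan annualises bleeds and consumption, so expressing AEs per unit of time would be in keeping with it.

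Three stronger inferences should not be drawn:

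- That extension AEs go unreported. They are in the combined tables and the planned listings.
- That the 3-to-24-month spread makes main-phase patients eightfold unequal in exposure. Patients who complete that phase without inhibitors do so at about 50 ED, so their drug exposure is similar even where calendar time differs.
- That every patient accrues the full 3.5 years of extension. That figure is a maximum, and staying on after 100 ED is optional and tied to commercial availability.

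**Conclusion.** The point holds as an inconsistency to reconcile together with an improvement to the AE summaries. The AE sentence in Section 18.2.4 conflicts with Sections 4.2 and 18.2.1. The planned summary tables cannot give the number of patients with an extension-phase AE, and their crude counts will be higher for the combined period simply because it is longer.

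The direction does not depend on the assumed rate; the size does. The ranges in the working rest on a constant rate of 0.1 to 1.0 per patient-year, which is not in the documents, and on maximum follow-up, so they illustrate the effect and do not forecast it. A reader might infer that the trial could never detect a change in AE rate over time. The documents do not support that: individual events will be listed and dose dates are collected, so the rates can be computed. They are just not planned.

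Priority is low, because AE frequency is a descriptive secondary endpoint and no hypothesis rests on it.

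**What to change.** In Section 18.2.4, add the extension phase to the AE/SAE sentence so that it names main, extension and combined, in agreement with Sections 4.2 and 18.2.1. If the sponsor means to leave it out, Section 4.2 should state the exception and its reason, and Section 18.2.1 should be aligned.

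In the same section, report AE and SAE events per patient-year of exposure (or per 100 ED) beside the existing counts for each of the three periods, and print the total exposure used as denominator. State which time scale is used, since calendar time and ED diverge in the main phase.

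The cost is one more set of columns and one rate per table. The data are already collected, and the only downside is a little more programming.

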2.48 Appendix B

The blood volume collected from the subject ~~for all tests~~ should not exceed 1% of the whole blood volume at any single time and 3% of whole blood volume in 28 days *according to This requirement is in line with European regulatory guidelines requirements (Directive 2001/20/EC)^{2,19} and FDA requirements, or it should be according to local guidelines for blood sampling volumes. As a reference, the table below shows the estimated blood volume in children weighing from 6 -25 kg and the blood volume that can be taken at any single time and within 28 days, respectively, according to EMA, European regulatory requirements (Directive 2001/20/EC) and over a 24h period according to FDA requirements guidelines.*

Total Blood volume according to Geigy Scientific Table and maximum blood sampling volume according to EMA and FDA.					
Weight (kg)	Blood volume (ml/kg)	Total Blood volume (ml)	Volume/blood sample (1%) EMA	Volume/28 days (3%) EMA	Volume/ 24h FDA
6	80	480	4.8	14.4	

7	80	560	5.6	16.8	14
---	---	---	---	---	
10	80	800	8.0	24.0	20
---	---	---	---	---	
15	80	1200	12.0	36.0	30
---	---	---	---	---	
20	80	1600	16.0	48.0	40
---	---	---	---	---	
25	80	2000	20.0	60.0	50

Substantial Protocol Amendment no 6

to Protocol, final version 3.0

dated 27 August 2012

Trial ID: NN7008-3809 (turoctocog alfa)

**Safety and Efficacy of turoctocog alfa in Prevention and Treatment of Bleeds in Paediatric
Previously Untreated Patients with Haemophilia A**

Trial phase: 3b

Applicable to all countries

Amendment originator:

Name: [REDACTED]

Department: Haemophilia. Clinical Operations FVIII & FXIII

This ~~confidential~~ document is the property of Novo Nordisk. ~~No unpublished information contained herein may be disclosed without prior written approval from Novo Nordisk. Access to this document must be restricted to relevant parties.~~

Table of contents

	Page
Table of contents	2
Table of tables	2
1 Introduction	3
1.1 Substantial protocol amendment.....	3
1.2 Rationale for amendment No. 6.....	3
2 Changes	5
2.1 1 Summary.....	5
2.2 2 Flow Chart	6
2.3 3.1.1.2 Risks and Benefits	7
2.4 5.1 Type of Trial	7
2.5 5.3 Treatment of Patients.....	8
2.6 6.2 Inclusion Criteria	8
2.7 6.3 Exclusion Criteria	8
2.8 6.5 Patient Replacement.....	8
2.9 6.6 Rationale for Trial Population	8
2.10 7 Trial Schedule	9
2.11 8.1.3 Visit 2.....	9
2.12 8.1.3.1 Combining Visit 1 and Visit 2	9
2.13 8.2.2 FVIII Inhibitors.....	9
2.14 8.2.3 FVIII Recovery Assessments	9
